IPA which has been widely used in studies addressing alcohol and other substance use behaviors (20).¹³ (13) The inclusion of this measure will allow us to better understand participant's social network characteristics of participants and whether they change over time as a function of the intervention. Childhood Sexual Abuse (CSA) (21): Numerous studies document a high prevalence of childhood sexual abuse (CSA) among HIV-positive gay and bisexual men, and has been associated with HIV risk and substance use behaviors (22, 23). We will administer an 8 item measure of CSA to better understand whether the intervention has a different impact on participants who have experienced CSA compared to those who have not

Collateral Reports. Collateral informants will be interviewed regarding the participant's drinking. These interviews will be confidential, and no information regarding the participant will be provided to the collateral. Collaterals will estimate the number of drinking days in the past month, the average number of drinks consumed per drinking day, and the number of heavy drinking days. They will indicate their level of confidence in their knowledge of the participant's drinking and only reports for which the collateral was at least "fairly confident" will be considered. The use of collaterals may increase honesty in reporting by participants and provides an index of the validity of self-reported drinking.

Measures of ART Adherence and Sexual Behavior

Timeline Followback (TLFB). The TLFB administered will be used to assess medication adherence and sexual risk behaviors as we have been doing in our current study. Due to the cognitive demands of completing a TLFB with alcohol, drug, sex, and adherence behavior, we will only go back 30 days from the interview for these measures. The TLFB has been shown to be a valid measure of adherence ^{14,15} and facilitates examination of alcohol-adherence associations on a daily basis ¹⁶⁻¹⁸. Participants will review each of the 30 days on the calendar, indicating the number of doses prescribed and taken each day. The dependent variable will be the percent of days with missed ART doses.

The TLFB interview for sex risk behaviors has previously been shown to be feasible, reliable, and valid ¹⁹, even in a high-risk population (psychiatric outpatients) ²⁰. In order to better assess sexual risk reduction strategies, this assessment asks whether their HIV-negative partners are on PrEP, in addition to whether participants engaged in other deliberate risk reduction strategies (i.e., strategic positioning, having oral instead of anal sex). This interview assesses each occasion of sexual activity over the past 30 days, with detailed information on the type of partner (long-term, dating, casual, or anonymous); HIV status of partner (positive, negative, or unknown); type of sexual activity (anal, insertive or receptive); condom use; and whether the participant was under the influence of alcohol and/or other substances. Three variables will be derived from this measure: occasions of unprotected anal intercourse (UAI), and occasions of UAI with a partner of negative or unknown status. The latter variable captures occasions of sex that carry the highest risk of HIV transmission ²¹.

Computer-Assisted Self Interviewing (CASI). We will use a brief CASI to provide a secondary assessment of alcohol, sex, and ART adherence that may reduce under-reporting of behaviors due to social desirability. The CASI queries behavior over the prior 6 months. The Sexual Risk Assessment queries the number and gender of partners with whom the participant reported having sex and the number of times the participant had unprotected insertive or receptive anal sex or vaginal sex with a partner of HIV-negative or unknown HIV status. The CASI also assess alcohol and drug use using a quantity-frequency interview, and adherence using a recent questionnaire that has recently been validated in a large sample of MSM by collaborators at Brown²².

Cross-behavioral measures. We will assess alcohol-ART interactive toxicity beliefs with a scale by Kalichman et al. that predicts non-adherence on drinking days ²³. We will assess motives for drinking ^{24,25}, including our newly validated scale for sexual drinking motives ²⁶.

Standard Clinical Assays and Research Biomarker Assessment

We will collect serum samples from all participants. Some clinical assays will be run in real time and will include immunologic profiling (CD4/CD8 enumeration) and complete blood count while others

including virologic assays (serologic HBV/HCV status, HIV-1 PVL and if required HBV, HCV viral loads) and a full liver profile (liver enzymes, bilirubin) will be processed and frozen before sent to labs for analysis. When possible and within the appropriate timeframe, all clinical values will be taken from patients' electronic medical records for patients who receive care at Fenway Health. For those who receive care at other health care facilities in the greater Boston or Miami area, we will ask their permission to request those values from their providers. Clinical lab values obtained through this study will be added to participants' medical records if they receive care at Fenway Health. For those receiving care at other health care facilities in the greater Boston area, we will request their permission to notify their providers of abnormal lab values. We also will use the samples to obtain serum biomarkers of inflammation (21-plex cytokine/chemokine assay); oxidative stress (4-HNE/LPO, 8-OHdG, AGE, carbonyl); insulin resistance and metabolic dysfunction; neurodegeneration (BDNF, ICAM, VCAM, GDNF, NGF, HGF, bFGF); and ceramide levels/profiles (see Virology Core for further details), as well as recent alcohol use (phosphotidyl ethanol). The non-clinical assays will be used only for research purposes and not entered into participants' medical records.

Measures of Neurocognitive Functioning

We will conduct a brief battery of neurocognitive tests that are likely to be sensitive to the effects of heavy alcohol consumption and HIV. The neurocognitive test results from baseline will be used for feedback for those in MI as we have been doing in our current study and has been done in other trials. The battery takes a total of 20 minutes to complete and includes the WTAR ^{27,28}, Trails A and B ²⁹, Digit Symbol ³⁰, Hopkins Verbal Learning test ³¹⁻³³, and the Controlled Oral Word Association Test ³⁴⁻³⁶. All of these measures are well-established neurocognitive measures that have each been widely used in numerous studies of HIV ³⁷⁻⁴¹ and alcohol ⁴²⁻⁵⁵ effects on brain functioning.

Measures of Treatment Utilization

Concurrent Treatment. Use of other treatments for alcohol or other substance use will be assessed including use of pharmacotherapy for excessive drinking (type and duration), number of sessions of counseling received for drinking or substance use, and the number of Alcoholics Anonymous or Narcotics Anonymous meetings attended. Those seeking alcohol or other substance use treatment beyond that offered in the study will be retained following the intent to treat principle.

Safety Monitoring

In an effort to meet the NIH policy for Data and Safety Monitoring, we have created a system for oversight of the project. Oversight of internal monitoring of the participants' safety will be conducted by the PI, [name]. Drs. [name] (Brown), [name] (Fenway Health), [name] (Fenway Health), and [name] (Florida International University (FIU), Miami) also will participate in the development and administration of the plan. Investigators on this application have extensive experience with clinical trials for excessive drinking and clinical and observational studies with HIV-infected patients.

Entities Conducting Monitoring:

The Institutional Review Boards (IRBs) at Brown University, Fenway Health, FIU, Jackson Memorial Hospital Medical Center, and the University of Miami will review this protocol and all procedures and will provide oversight. Monitoring will be done by the Principal Investigator, [name], the Brown University IRB, and the respective site IRBs. Drs. [name], [name], [name], and [name] (Co-I's) will also participate in the administration of the monitoring plan. What is Monitored?

Monitoring is done of all procedures to ensure that they conform to the approved protocol; of unforeseen circumstances that might arise and affect safety; of all reports of serious adverse events as defined in 38 CFR 46 and the FDA 312.32 (death, life-threatening experience, new or prolonged hospitalization, persistent or significant disability/incapacity); of other significant adverse events

(adverse events that lead to drop out by participant or termination by the investigator); of unexpected adverse events resulting from the study; and of expected adverse events.

Monitoring is done of all study inclusion and exclusion criteria. During this clinical trial, we will notify officials, as mandated by law, if a participant reports intentions to harm him/herself or others, or reports child abuse or abuse of an elder. The PI ([name]) is a licensed clinical psychologist, who will be available on call in case of any psychological adverse events. In the event a participant were to report a need or interest in treatment for alcohol/substance dependence, psychiatric disorder, or distress, an appropriate referral to resources will be provided based on an extensive list of referral resources maintained at each study site.

Frequency of Monitoring:

All adverse events will be continuously monitored by the PI. Participants will be given contact information so that they can inform us of events that occur in between study visits. [name] will conduct daily oversight of participant safety. He will videoconference weekly with staff to review participant progress and their experiences with the experimental procedures, including adverse events. Any adverse events that are observed and/or reported will be immediately reported to [name]. The Investigators will be available to meet outside of the weekly meetings, if necessary, due to concerns regarding a particular participant or any problems that may arise for participants. If necessary, they will make appropriate recommendations for changes in protocol.

The Brown University and collaborating IRBs conduct the monitoring at the continuing reviews as scheduled, whenever modification requests are considered, and upon receiving reports of serious adverse events from the PI or anyone else. NIAAA monitors the study upon receipt of annual progress reports and whenever other information is received.

Reporting Plan:

Any serious adverse events that are observed and/or reported will be immediately reported to [name]. Unexpected serious adverse events are reported to Brown University, the site IRBs, and to NIH by telephone and by written report within 48 hours of our receipt of information regarding the event. All other adverse events related to the study will be reported at the continuing review. All serious adverse events related to the study will be reported annually in the Progress Report sent to the NIAAA Project Officer.

Any actions taken by the IRB, other than acceptance of the adverse event report, will be reported to NIAAA along with any changes or amendments to the protocol requested by the IRB in response to these reports. Proposed changes or amendments to the protocol in general must be requested first in writing to the Brown and site IRBs, which will then grant or deny permission to make the requested change or amendment in protocol. NIAAA will subsequently be informed of any substantive changes or amendments in approved protocol.

Data Quality Assurance and Confidentiality

(a) Procedures to ensure the validity and integrity of the data. Several procedures currently in practice in our laboratory will also be utilized for this study to guarantee the validity, integrity, accuracy, and completeness of the data. It will be made clear to all participants that all information obtained during assessments is confidential.

(b) Procedures to guarantee the accuracy and completeness of the data during data collection, transmission, and analysis. First, the Data Coordinator will review each file within 2 weeks of data collection for completeness, accuracy, and validity of responses. All scanned data will be verified by the Data Coordinator using a computerized verification program. Data files are accessible only to project personnel and are password protected. The Data Coordinator will review the distributions of all raw data to ensure that data are within range and to check missing data with the hard copy of the data. The project database (including uploaded data files from the computer (CASI), text messaging database and scanner machine) is password protected and accessible only to the project's Data Coordinator, staff members on the project, and members of the Biostatistics Core.

(c) Procedures to maintain confidentiality. Study staff will maintain strict confidentiality regarding all aspects of a subject's participation in this study. Any individual information gathered in the course of the study will not be discussed with anyone who is not directly involved with this study. For each stage of the research, participant names and contact information will be maintained in a

recruitment/enrollment database during the course of the study. Once individuals enroll in the study, names will be linked to participant ID number in this database, which will be kept in a restricted access folder on a secure server. This file will be assigned a code name unrelated to the name of the study. Signed consent forms will be kept in a locked file cabinet, separate from any other project data. Once data collection is completed, the corresponding recruitment/enrollment database will be deleted as it is unnecessary to maintain the link between participant identity and study data. All information collected as part of this study will be accessible only to research staff who have completed mandatory training in the protection of human subjects.

Potential Risks to Participants

Potential risks in the study are considered low and include: (1) potential discomfort related to completing questionnaires about sensitive information such as sexual behavior and alcohol/drug problems, (2) potential discomfort during blood draws for viral load, CD4, and liver function tests, (3) potential breach of confidentiality and/or privacy; (4) symptoms of alcohol withdrawal.

Protection against Risks

Potential risks of the study are considered low. For the possibility of subjective discomfort from answering questions, any distress will be minimized by assurance that participants can refuse to answer any question that they do not feel comfortable addressing and may withdraw at any time without penalty. Interviewers are skilled in talking about sensitive information with subjects, and subjects may decide to end an interview at any time. In the unlikely event that a participant experiences considerable distress we will make a referral (if needed) for clinical assessment and/or counseling provided onsite. Subjects will be asked to provide urine and blood samples for testing. Potential discomfort during the blood draw and urine collection will be explained during informed consent. Subjects can choose to withdraw from the study without penalty.

Confidentiality is maintained as follows. Data files recorded with a participant identification number will be stored at their respective clinics; Fenway Health in Boston and JMHMC in Miami. These files are accessed only by project staff, who will be either Fenway Health, JMHMC, or Brown University employees. All project staff are knowledgeable about confidentiality and human subjects protection. Follow-up contact forms that require identifying information are stored separately from data files and are accessed only by those staff conducting follow-up interviews. Information about participants that is needed for intervention delivery will be collected by staff at Fenway Health or JMHMC and uploaded without identifying information to a secure Brown folder. Brown staff conducting videoconferences with participants will do so in room that is private from other Brown staff. The videoconference software used is HIPAA compliant. During follow-up telephone calls to the participants' homes, no information is provided to others in the household. All blood samples are identified by subject ID number only before being sent to the Virology Core for testing. Data files contain no identifying information, including date of birth and town of residence. Data are transmitted to the Data Core at the Center for Statistical Sciences in encrypted format.

All text messages sent from subjects to our phone number will be catalogued and encrypted, stored per Brown University security standards. Once received the responses from each participants will be separated from the cell phone number and identified only by ID number. All participants will be advised to set up password protection on their cell phones and to erase messages after responding to

minimize the chance of loss of private information. We state explicitly in the consent that we will not be able to respond in real-time to any concern a participant has that is outside the expected responses that is sent to our phone number, nor any text message outside the scope of the question we ask.

Breach of confidentiality is highly unlikely because all information will be identified with a numeric code only and stored in a locked file cabinet. An enrollment database linking names and study identification numbers will be kept in a secure folder separate from other subject data sources and will be used to facilitate the collection of follow-up data. Only grant staff will have access to this database. All staff are or will be fully trained in relevant ethical principles and procedures, including confidentiality. All assessment and treatment procedures will be closely supervised by the PI. All audiotapes will be erased upon completion of data analysis.

Some subjects may experience mild to moderate symptoms of alcohol withdrawal such as insomnia, psychomotor agitation, or hand tremor if they choose to stop or substantially reduce drinking; however, more significant withdrawal symptoms will be unlikely given our exclusion criteria. Specifically, we will exclude individuals who show clinically significant alcohol withdrawal at baseline after abstaining from alcohol for 24 hours. Given our exclusion criteria, any alcohol withdrawal symptoms are likely to be mild to moderate in intensity and transient.

During this clinical trial, we will notify officials, as mandated by law, if a participant reports intentions to harm him/herself or others, or reports child abuse or abuse of an elder. If a participant reports current suicidal ideation when completing the MINI, the participant will be evaluated by [name] (or another licensed clinical professional) at Fenway Health or a licensed clinical professional at JMHMC before being ruled out of the study.

Our rigorous screening procedures will help to ensure that consenting volunteers are recruited who do not report significant psychiatric disturbance. However, in the event a participant were to report a need or interest in treatment for substance dependence, psychiatric disorder, or distress, an appropriate referral to resources will be provided. We have included a description of the plan for data and safety monitoring of the research and adverse event reporting to ensure the safety of participants.

Potential Benefits of the Proposed Research to the Subjects and Others

As part of their participation in the study, participants will receive a brief intervention which could lead to reduced hazardous drinking. Furthermore, subjects will be participating in a study that may provide knowledge to guide the future treatment of HIV-infected patients who drink heavily. Given that the risks to subjects are considered to be minimal, the risk-benefit ratio is deemed favorable.

In addition, this study has the potential to contribute valuable information about the potential for brief alcohol interventions to reduce drinking in patients in HIV primary care and about the effects of reducing drinking on a range of important HIV-related biomedical and behavioral outcomes. Developing effective interventions that address alcohol use in HIV patients can make a major public health impact by reducing the morbidity, mortality, and transmission risk associated with heavy alcohol use. Given the substantial health risks associated with heavy drinking in HIV patients and the relatively minor risks to subjects, the importance of the potential knowledge to be gained relative to the subject risk is favorable.

Alternative treatments. Participants will be randomized to receive a brief alcohol intervention in addition to their standard HIV care. Alternative alcohol treatments are available in the Boston and Miami areas, including specialized addictions treatment services housed within Fenway Health and JMHMC. Individuals desiring additional treatment for alcohol problems will be given appropriate referrals.

Informed Consent

All participants will be fully informed of the purposes and procedures of the study. Research interviewers will describe the screening and the study to potential participants, including that if they are eligible and then agree to participate, they will be re-contacted over the following twelve months, that

they are paid for completing the follow-up interviews, that the information they provide is kept confidential, and that they may withdraw at any time without penalty. If an individual wishes to participate, he will be asked to sign an informed consent form prior to completing the baseline assessment. Participants are provided with a copy of the consent forms, and the originals are kept in locked files at Fenway Health and JMHMC.

Statistical Analysis Plan

For primary outcomes—(a) drinks per week and (b) number of heavy drinking at 6- and 12months follow-ups—we fit marginalized zero-inflated negative binomial (MZI-NB) models to test the main and interactive effects of each of the three factors in the study design:

 $log \{E(Y)\} = \beta_0 + \beta_1 A + \beta_2 B + \beta_3 C + \beta_{12} AB + \beta_{23} BC + \beta_{13} AC + \beta_{123} ABC + \gamma X.$ (Eq1) with a similar logit model describing the excess zeros as in the traditional zero-inflation model. The terms *A*, *B*, and *C* in Eq1 are dummy variables for BI vs. MI, no ITM vs. ITM, and no EI vs. EI; and coded orthogonally so they can be evaluated concurrently with the three 2-way interactions and one 3-way interaction among these factors. The model parameters β_1 , β_2 and β_3 capture the main effects, and $\beta_{13}, \ldots, \beta_{123}$ capture the two- and three-way interaction effects. The models are adjusted for baseline covariates *X*, including the baseline value of the dependent variable, recruitment site, and indicators for interventionists. Following intention-to-treat principles, we conduct regression analyses on all participants who were randomized to an intervention condition regardless of the number of sessions of intervention they completed.

Secondary outcomes for this study are: (1) the number of days engaging in condomless sex with a non-steady partner in the past 30 days at 6 and 12 months, (2) percentage of the past 30 days taking all prescribed ART doses at 6 and 12 months, and (3) HIV viral suppression (i.e., <20 copies/ml) at 12 months. Due to limited variation in condomless sex and ART adherence outcomes, we dichotomize these, respectively, as: (a) 0 day vs \geq 1 day of condomless sex with non-steady partner and (b) \geq 95% ART adherent [i.e., perfect or near-perfect adherence] vs < 95% ART adherence. For secondary outcomes, logistic regression models, similar to the model above but replacing the left-hand side of Eq1 by *h*{*E*(*Y*)} with *h*(.) being the logit link function, were used to test the main and interactive effects of the three study factors.

Missing data. We conducted our primary analyses using complete data. We also used re-ran analyses with imputed data as a sensitivity analysis. Imputation of missing data was carried out using the chained-equation method (R MICE package) assuming that data were missing at random. We maintained the longitudinal structure of the data and built imputation models that imputed missing values at 6 months only using baseline data and observed 6-month data, and imputed the missing values at the 12 months using baseline and imputed 6-month data and observed 12-month data. Imputations were iterated until the distribution of imputed values stabilized. Five complete datasets were created and used for regression analyses. The results were then pooled using Rubin's method^{56,57}.

References

- 2. Radloff LS. The CES-D scale: A self-report depression scale for research in the general population. *Applied Psychological Measurement*. 1977;1(Summer):385-401.

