All participants in the main trial, regardless of treatment condition, will be assessed on a variety of interview, self-report, and biochemical measures at 6 and 12 months after the baseline interview. Interviewers conducting follow-ups will be different from those conducting the baseline session when feasible and will not be informed of subjects' treatment condition assignment. To ensure that the accuracy of self-reports is not affected by intoxication, alcohol breathanalysis will be conducted at all assessments. Subjects with a BrAC > .02 g/dl (an alcohol level that may affect assessment) will not be assessed and their follow-up appointment will be re-scheduled for the following day or at the next available time. All subjects will provide serum samples at each follow-up.

In order to maximize study participant retention, we will offer follow-up 6- and 12-month visits by phone for any participant who, in the course of the 12-months of study participation, moves to a location that makes it impossible to travel to Fenway Health or JMHMC for in-person visits. These phone visits will include a subset of assessments as well as referrals for mental health or substance abuse services. In addition, for those participants in EI, they will be given counseling by phone at the 6-month visit rather than by videoconference. We will then mail the full compensation check to an address specified by the participant. Participants will be compensated \$100 for the baseline interview, \$50 for the 6-month interview, and \$60 for the 12-month interview, for a total of \$210 in the form of checks or gift cards. Those found ineligible at baseline will be compensated \$50 for their time given the eligibility is confirmed within the first half of the baseline interview. Participants will also receive a Charlie Ticket in the amount of the cost of a round-trip T ride at each study visit that they attend in person.

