We will obtain complete demographic information on each participant who is eligible and will also assess depressive symptoms using the Center for Epidemiologic Studies – Depression scale [CES-D;²]. Depressive symptoms, which can sometimes result from excessive alcohol consumption, have been associated with poor ART adherence and are therefore important to assess as a covariate. The Treatment Services Review will assess use of major medical care outside of the health care facility where the participant normally receives care. Internet and Communication Use (use of technology) will be asked in order to learn what means of communication may be most effective in administering interventions in this population and whether there are potential barriers to the text messaging program. We will also ask participants how often they accessed the ReACH project website for information on alcohol use and HIV in the past 6 months. Experienced discrimination due to HIV status, race/ethnicity, and sexual orientation will be assessed with the Multiple Discrimination Scale³. Internalized homonegativity will be measured using a 5-item subscale from the Lesbian, Gay, and Bisexual Identity Subscale (Mohr & Fassinger, 2000).

Measures of Alcohol Use and Problems, Other Substance Use, and Motivation to Change

We will gather information about age of onset of alcohol use, period of heaviest drinking, most drinks consumed on a single day, and number of lifetime drug classes used. Current and past alcohol and substance use disorders (as well as screening for mania and psychosis) will be assessed at baseline using the MINI 7.0.1⁴. Urine Drug Screen. In addition to providing a breath sample for alcohol concentration analysis at each in-person assessment, participants also will provide a urine sample for testing for recent

drug use: PCP, ecstasy, barbiturates, methadone, oxycodone, benzodiazepines, methamphetamine, THC, opiates, and cocaine. Alcohol withdrawal symptoms will be assessed using the Clinical Institute Withdrawal Assessment for Alcohol, revised ¹.

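### Phone follow-up is offered only on relocation and is not said to include the TLFB, so a local non-attender has no stated route to the interview-based primary outcomes

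*Combined protocol and SAP*

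**What the plan says.** The Follow-up Assessments section makes both later visits available by phone under a single condition, which is that the participant "moves to a location that makes it impossible to travel to Fenway Health or JMHMC for in-person visits". The stated aim is retention. No other section adds a second ground. On content the section says "These phone visits will include a subset of assessments", together with referrals, and does not list the subset.

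The same section sets a breath-test threshold of 0.02 g/dl at follow-up. Participants above it "will not be assessed and their follow-up appointment will be re-scheduled for the following day or at the next available time". No limit on attempts is given. It also says "alcohol breathanalysis will be conducted at all assessments", whereas the section on measures of alcohol use speaks of "providing a breath sample for alcohol concentration analysis at each in-person assessment".

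If a visit has not been scheduled after at least three contact attempts, or by the last two weeks of the visit window, staff write to collateral informants and then interview them about the participant's drinking. The protocol uses these reports to corroborate self-report and to index its validity.

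The SAP's missing-data paragraph says "We conducted our primary analyses using complete data". A sensitivity analysis uses chained-equation imputation under missing at random, with five datasets built from baseline and earlier follow-up data.

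**The concern.** Both primary outcomes, drinks per week and heavy drinking at 6 and 12 months, describe recent drinking. The TLFB section says this interview supplies drinks per week and the percentage of heavy drinking days over the past 30 days. None of that needs a clinic procedure, and the trial already telephones every participant for counselling at 1 month. Yet the phone visit depends on where the participant lives, not on whether the outcome is about to be lost.

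The outcomes lost this way are partly avoidable, and non-attendance may be related to current drinking. A complete-data analysis drops these participants. Imputation under missing at random brings them back only on the assumption that, given the observed data, their drinking resembles that of attenders. Loss could also differ by factor: extended-intervention participants have calls at 3 and 9 months and a counselling session tied to the 6-month appointment, and the others do not.

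**Working it through.** **Routes to a drinking interview, as written**

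| Participant | Stated route | Gap |
|---|---|---|
| Moved out of reach | Phone visit | TLFB not named in the subset |
| Local, does not attend | Repeated contact attempts, then collaterals | No phone interview of the participant |
| Above 0.02 g/dl at the visit | Re-scheduled, no cap | Outcome lost only if never assessed before the window closes |

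Two other sources do not fill the second row. Collateral reports appear nowhere in the SAP as outcomes or imputation inputs, and participants may decline to name a collateral. Weekly text reports after day 30 exist only for participants assigned to both text messaging and the extended intervention, and they are not named as outcome data.

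**What can be reproduced.** The counts agree: 2 × 112 = 224, or 112 per level of each factor. The documents state no alpha, power, effect size, SD or dropout rate, so there is no planned figure to check. Everything below rests on assumed rates.

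**Outcomes at stake.** With 10% and 20% missing, 0.10 × 224 ≈ 22 and 0.20 × 224 ≈ 45. If one third of the 22 to one half of the 45 could be reached by phone, 7 to 22 outcomes are recovered.

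**Precision.** This uses a normal approximation with two-sided alpha 0.05 and 80% power. Detectable difference = (1.96 + 0.84) × √(2/n) SD, with n per factor level.
- n = 112: 0.374 SD
- 10% missing, n = 100.8: 0.395 SD; power at 0.374 SD falls to 76%
- 20% missing, n = 89.6: 0.419 SD; power at 0.374 SD falls to 71%

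**Bias with no true effect.** Let a fraction m be missing in each arm and let non-attenders drink k times the attenders' mean. With the true mean set to 1 in both arms, the attenders' mean is 1 / [(1 − m) + mk]. The complete-data ratio (arm with less loss over arm with more) is then:
- 5% vs 15% missing: 1.075/1.025 = 1.05 (k = 1.5); 1.15/1.05 = 1.10 (k = 2); 1.30/1.10 = 1.18 (k = 3)
- 10% vs 20% missing: 1.10/1.05 = 1.05; 1.20/1.10 = 1.09; 1.40/1.20 = 1.17
- 10% in both arms, same k: ratio 1.00, but mean drinking is understated by 5%, 9% and 17%

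**An extreme case, and how much the phone visit would remove.** Both arms have 80% at 15 and 20% at 25 drinks per week, a true mean of 17. One arm loses 10% and the other 20%, all from the heavier group.
- No recovery: (0.8×15 + 0.1×25)/0.9 = 16.11 and (0.8×15)/0.8 = 15.00. The ratio is 0.93, a false 7% reduction.
- Half recovered: (12 + 0.15×25)/0.95 = 16.58 and (12 + 0.10×25)/0.90 = 16.11. The ratio is 0.97.
- One third recovered: (12 + 0.1333×25)/0.9333 = 16.43 and (12 + 0.0667×25)/0.8667 = 15.77. The ratio is 0.96.

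The false reduction shrinks to about 3-4%. It does not vanish.

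**The case against.** A reader might infer that the breath-test rule removes heavier drinkers from follow-up, and that anyone who fails it should be telephoned instead. The documents do not support this. A failed test defers the visit with no cap on attempts, and follow-up tolerates up to 0.02 g/dl where baseline requires 0.00. Loss arises only for someone who keeps failing or does not return before the window closes, and no rate is given, so that group may be close to empty. The test exists to keep intoxication from distorting self-report. An unverified call to people who have just failed it would trade missing data for doubtful data.

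A reader might also take 7% as the likely bias. It needs every missing person to be a heavier drinker, one arm to lose all of its heavier drinkers, and a 2:1 imbalance in loss. It also ignores the SAP's adjustment for baseline drinking.

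Other points against carry some weight:
- The plan makes real retention efforts: at least three contact attempts, collateral letters, paid visits, travel tickets and scheduling around dental appointments. None of these produces an outcome from someone who still does not attend.
- The imputation analysis uses baseline and 6-month data and is a partial answer. It does not cover loss that depends on unobserved current drinking.
- Some people who will not attend may also refuse a call, so the recovery fractions are uncertain.
- The document is dated April 2024, and its missing-data paragraph is in the past tense. If follow-up is over, a new trigger recovers nothing. That limits when the change can be used, but it does not make the rule sound.

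**Conclusion.** The point holds as a gap in outcome collection. Relocation is the only stated ground for a phone visit, though the text does not use the word only; the restriction follows because no other ground appears. A local non-attender has no stated route to the primary outcomes, and even movers are not assured of them because the phone subset does not name the TLFB. That the primary outcomes come from the TLFB is read from the measures section, since the SAP does not name the instrument.

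The size is unknown. Under the assumed rates, 7 to 22 outcomes could be recovered. Spurious ratios of about 1.05 to 1.18 need loss that is both unequal by arm and related to drinking. With equal loss and equal selection the comparison is unbiased in that simple model, and only the level of drinking is understated. The change is worth making because it is cheap and reduces missing data at source. It would lessen a bias of this kind, not remove it.

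**What to change.** In Follow-up Assessments, offer the phone visit to any participant not seen in person by the last two weeks of the visit window, the point at which collateral contact already begins. State that the alcohol TLFB is collected first at every phone visit, including those for movers. Record the mode of assessment, and report the primary result with and without phone-collected outcomes.

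For visits deferred on the breath test, keep re-scheduling as the route and report by arm the outcomes lost for this reason. Reconcile the two statements on where breath samples are taken (all assessments, or each in-person assessment), so that it is clear what applies to a phone visit.

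If follow-up has already closed, report missing primary outcomes by arm, reason (including breath-test deferral) and mode.

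The cost is mainly protocol wording and some interviewer time, since a phone visit and its payment already exist. The downside is mixed interview modes and no breath or blood sample at those visits, which the plan already accepts for movers.
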